6.3.5. Local Tolerability Scale

At each specified study visit, the Investigator (or qualified evaluator) will assess the presence and overall degree of irritation at the application sites, according to the LTS (an example of the LTS is provided in [Appendix 8](#)). The score will ideally represent an “average” across all application sites. To the fullest extent possible, the same Investigator (or designated evaluator) will perform all tolerability assessments for an individual subject throughout the study. If the subject is applying study treatment to “sensitive areas” (eg, genitals, face, neck, and skin folds), then the degree of irritation for these areas should also be assessed by the investigator.

Additionally, at each specified study visit, the participant will use a 5-point LTS to assess the presence and degree of burning/stinging and itching at the treatment areas. The score will ideally represent an “average” across all application sites.

6.4. Treatment of Study Drug Overdose

For this study, accidental or intentional oral ingestion of drug product will be considered an overdose. Ingestion of a 30-gram tube of tapinarof cream, 1% would result in an oral dose of 300 mg.

The Sponsor does not recommend specific treatment for an overdose; however, in the event of an overdose, the Investigator (or treating physician) should do the following:

- Contact Medical Monitor to discuss the event
- Closely monitor the subject for AEs/SAEs and laboratory abnormalities
- Provide general symptomatic treatment as necessary
- Document the quantity of the excess dose as well as the duration of the overdosing in the eCRF.
- If the Medical Monitor requests a plasma sample for PK analysis, then a blood sample for PK should be obtained within 2 days from the date of the last dose of study drug.

Decisions regarding dose interruptions or modifications following an overdose will be made by the Investigator in consultation with the Medical Monitor based on the clinical evaluation of the subject.

6.5. Pharmacokinetics

A single blood sample for PK analysis of tapinarof cream, 1% will be collected at a subset of sites in a subset of subjects at timepoints indicated in the Schedule of Assessments (Table 1) and Section 7. The actual date and time of each blood sample collection will be recorded as well as the date and time of the last dose of study drug prior to sample collection. Collection, processing, storage, and shipping procedures are provided in the Laboratory Manual.

Concentrations of tapinarof will be determined in plasma samples using a validated bioanalytical method. Raw data will be archived at the bioanalytical site.

7. TIMING OF PROCEDURES AND ASSESSMENTS

This section lists the procedures and assessment to be performed at scheduled timepoints during the study as outlined in the Schedule of Assessments (Table 1). Information on study procedures and assessments is provided in Section 6.

- Any change in timing or any addition of a timepoint(s) for any planned study assessment must be documented in a “Note to File,” which is approved by the relevant Sponsor study team member and then archived in the study Sponsor and site study files; this will NOT constitute a protocol amendment.
- The IRB/IEC will be informed of any safety issues that require alteration of the safety monitoring scheme or amendment of the Informed Consent Form (ICF).

NOTE: Assessments and procedures should be performed predose on clinic visit days.

7.1. Visit 1; Screening Period (Day -34 to Day -1)

After the subject has signed the Informed Consent Form (ICF), potential study subjects will undergo Screening procedures and assessments to confirm eligibility to participate in the study. Screening assessments will include the following:

- Demography recording
- Serum pregnancy test (females of child-bearing potential)
- Medical history recording
- ECG recording
- Brief physical examination (including weight, height, and body mass index [BMI])
- Vital signs measurements
- HADS assessment
- PGA score
- %BSA affected calculation; subject’s scalp, palms, and soles should be excluded from the %BSA calculations used to determine patient’s eligibility
- Blood sample collection for clinical laboratory tests (serum chemistry, hematology, diagnostic tests)
- Urinalysis
- AE recording (from the time the ICF is signed)
- Concomitant medication recording (from the time ICF is signed)

To determine subject eligibility at Screening, a single repeat of tests or procedures may be allowed at the discretion of the Investigator. The Medical Monitor should be consulted if needed.

7.2. Visit 2; Baseline (Day 1)

On Day 1, subjects will be reassessed to confirm continued eligibility to participate in the study. All subjects who continue to meet study eligibility criteria will be randomized to treatment.

The following additional procedures and assessments will be performed at the Baseline Visit:

- Urine pregnancy test (females of child-bearing potential)
- Changes to medical history will be recorded
- Brief physical examination
- Vital signs measurement
- Photography of a representative area of the subject's disease area (optional; at a subsection of study sites)
- PGA score
- %BSA affected calculation (performed before PASI); subject's scalp, palms, and soles should be excluded from the %BSA calculations used to confirm patient's eligibility
- PASI
- DLQI
- SF-36
- PSD
- Peak Pruritus-NRS
- AE recording
- Concomitant medication recording (from the time ICF is signed)
- Diary dispensed (subjects will be instructed in how and when to complete diary)
- Subject randomized to study treatment and registered in IVRS
- Study drug dispensed
- Instruction on how to apply study drug
- Study drug application under supervision

7.3. Double-Blind, Vehicle-Controlled Phase

Subjects will return to the study site at Weeks 2, 4, 8, and 12 and will be contacted by phone at Weeks 6 and 10 of the double-blind phase of the study.

7.3.1. Visit 3; Week 2 (Day 15 ±2 Days)

The following procedures and assessments will be performed at Visit 3:

- Vital signs
- PGA score
- %BSA affected calculation (performed before PASI)
- PASI
- LTS
- PSD

- Peak Pruritus-NRS
- AE recording
- Concomitant medication recording
- Collect and dispense subject diaries
- Review subject diaries for treatment compliance
- Collect and dispense study drug
- Review instructions on how to apply study drug
- Study drug application under supervision

7.3.2. Visit 4; Week 4 (Day 29 ±2 Days)

The following procedures and assessments will be performed at Visit 4:

- Urine pregnancy test (females of child-bearing potential)
- Brief physical examination
- Vital signs measurement
- Photography of a representative area of the subject's disease area (optional; at a subset of study sites)
- Blood sample collection for PK analysis (subset of sites and subjects)
- Blood sample collection for clinical laboratory tests
- PGA score
- %BSA affected calculation (performed before PASI)
- PASI
- LTS
- DLQI
- SF-36
- PSD
- Peak Pruritus-NRS
- AE recording
- Concomitant medication recording
- Collect and dispense subject diaries
- Review subject diaries for treatment compliance
- Collect and dispense study drug
- Review instructions on how to apply study drug
- Study drug application under supervision

7.3.3. Visit 5; Week 8 (Day 57 ±2 Days)

The following procedures and assessments will be performed at Visit 5:

- Urine pregnancy test (females of child-bearing potential)
- Brief physical examination

- Vital signs measurement
- Photography of a representative area of the subject's disease area (optional; at a subset of study sites only)
- PGA score
- %BSA affected calculation (performed before PASI)
- PASI
- LTS
- PSD
- Peak Pruritus-NRS
- AE recording
- Concomitant medication recording
- Collect and dispense subject diaries
- Review subject diaries for treatment compliance
- Collect and dispense study drug
- Review instructions on how to apply study drug
- Study drug application under supervision

7.3.4. Visit 6; Week 12 (Day 85 ±2 Days)

The following procedures and assessments will be performed at Visit 6:

- Urine pregnancy test (females of child-bearing potential)
- Brief physical examination
- Vital signs measurement
- Photography of a representative area of the subject's disease area (optional, at a subsection of study sites)
- Blood sample collection for PK analysis (subset of sites and subjects)
- Blood sample collection for clinical laboratory tests
- PGA score
- %BSA affected calculation (performed before PASI)
- PASI
- LTS
- DLQI
- SF-36
- PSD
- Peak Pruritus-NRS
- AE recording
- Concomitant medication recording
- Collect subject diaries
- Review subject diaries for treatment compliance

- Collect study drug

7.3.5. Phone Contact at Weeks 6 (Day 43 ±2 Days) and 10 (Day 71 ±2 Days)

Subjects will be contacted by phone at Weeks 6 and 10 to review study drug application instructions and to record AEs and concomitant medication use. Subjects should be reminded to complete their daily diary and bring it with them to the next clinic visit.

7.4. Follow-Up Visit 7; Week 16 (Day 113 ±4 Days)

Subjects who do not enroll in the open-label long-term study will return to the study site at Week 16 to complete follow-up assessments as follows:

- Urine pregnancy test (females of child-bearing potential)
- Brief physical examination
- Vital signs measurement
- Blood sample collection for clinical laboratory tests
- Urinalysis
- PGA score
- %BSA affected calculation (performed before PASI)
- PASI
- LTS
- DLQI
- SF-36
- PSD
- Peak Pruritus-NRS
- AE recording
- Concomitant medication recording

7.5. Early Termination Visit

Subjects who withdraw early from the study will be asked to return to the study site to complete Early Termination assessments as follows:

- Urine pregnancy test (females of child-bearing potential)
- Brief physical examination
- Vital signs measurement
- Blood sample collection for clinical laboratory tests
- Urinalysis
- PGA score
- %BSA affected calculation (performed before PASI)
- PASI
- LTS
- DLQI

- SF-36
- PSD
- Peak Pruritus-NRS
- AE recording
- Concomitant medication recording
- Collect subject diaries
- Review subject diaries for treatment compliance
- Collect study drug

7.6. End of Study

The end of study is defined as when the last active subject has completed the Week 16 Follow-up Visit 4 weeks after the end of treatment (if subject does not enroll in the separate long-term study) OR the last active subject has completed the 12 weeks of treatment in this study (if subject is eligible and enrolls in the separate long-term study).

8. SAFETY MONITORING AND REPORTING

8.1. Adverse Events, Serious Adverse Events, and Adverse Events of Special Interest

The Investigator or site staff is responsible for detecting, documenting, and reporting events that meet the definition of an AE, SAE, or adverse events of special interest (AESIs). At each visit/contact, subjects should be questioned in a general way so as not to introduce bias in detecting AEs and/or SAEs. Open-ended and non-leading verbal questioning of the subject is the preferred method to inquire about AE occurrence.

Investigators are not obligated to actively seek AEs or SAEs in former study subjects. However, if the Investigator learns of any SAE, including a death, at any time after a subject has been discharged from the study, and he/she considers the event reasonably related to the study drug or study participation, the Investigator should promptly notify the Sponsor.

8.1.1. Definition of Adverse Events

An AE is any untoward medical occurrence in a Subject temporally associated with the use of a medicinal product, whether considered causally related or not related to the medicinal product.

An AE can therefore be any unfavorable and unintended sign (including an abnormal laboratory finding), symptom, or disease (new or exacerbated) temporally associated with the use of a medicinal product.

Events meeting the definition of an AE **include**:

- Any abnormal laboratory test results (hematology, clinical chemistry) or other safety assessments (eg, vital signs measurements), including those that worsen from baseline, and felt to be clinically significant in the medical and scientific judgment of the Investigator
- Exacerbation of a chronic or intermittent pre-existing condition (eg, atopic dermatitis) including either an increase in frequency and/or intensity of the condition
 - For skin-related AEs, it should be noted whether or not the event is in the area of active application of study drug, and/or if spreading beyond the application site.
- New conditions detected or diagnosed after study drug administration even though it may have been present prior to the start of the study
- Signs, symptoms, or the clinical sequelae of a suspected interaction
- Signs, symptoms, or the clinical sequelae of a suspected overdose of either study drug or a concomitant medication (overdose per se will not be reported as an AE/SAE)
- "Lack of efficacy" or "failure of expected pharmacological action" per se will not be reported as an AE or SAE. Such instances will be captured in the efficacy assessments. However, the signs, symptoms, and/or clinical sequelae resulting from lack of efficacy will be reported as AE or SAE if they fulfill the definition of an AE or SAE.
- Symptomatic complaints at the site of local application (eg, burning/stinging, pruritus, and erythema)

Events that **do not** meet the definition of an AE include:

- Any clinically significant abnormal laboratory findings or other abnormal safety assessments that are associated with the underlying disease, unless judged by the Investigator to be more severe than expected for the subject's condition
- The disease/disorder being studied or expected progression, signs, or symptoms of the disease/disorder being studied, unless more severe than expected for the subject's condition
- Medical or surgical procedure (eg, endoscopy, appendectomy); the condition that leads to the procedure is an AE
- Situations where an untoward medical occurrence did not occur (social and/or convenience admission to a hospital)
- Anticipated day-to-day fluctuations of pre-existing disease(s) or condition(s) present or detected at the start of the study that do not worsen

8.1.2. Definition of Serious Adverse Event

If an event is not an AE per Section 8.1.1, then it cannot be an SAE even if serious conditions are met (eg, hospitalization for signs/symptoms of the disease under study, death due to progression of disease, etc.).

An SAE is any untoward medical occurrence that, at any dose:

- Results in death
- Is life-threatening
 - The term “life threatening” refers to an event in which the subject was at risk of death at the time of the event. It does not refer to an event, which hypothetically might have caused death, if it were more severe.
- Requires hospitalization or prolongation of existing hospitalization
 - In general, signifies that the subject has been detained (usually involving at least an overnight stay) at the hospital or emergency ward for observation and/or treatment that would not have been appropriate in the physician's office or outpatient setting. Complications that occur during hospitalization are AEs. If a complication prolongs hospitalization or fulfills any other serious criteria, the event is serious. When in doubt as to whether “hospitalization” occurred or was necessary, the AE should be considered serious.
 - Hospitalization for elective treatment of a pre-existing condition that did not worsen from baseline is not considered an AE.
- Results in disability/incapacity: a substantial disruption of a person's ability to conduct normal life functions.
 - This definition is not intended to include experiences of relatively minor medical significance such as uncomplicated headache, nausea, vomiting, diarrhea, influenza, and accidental trauma (eg, sprained ankle) which may interfere or prevent everyday life functions but do not constitute a substantial disruption.
- Results in a congenital anomaly/birth defect
- Medical or scientific judgment should be exercised in deciding whether reporting is appropriate in other situations, such as important medical events that may not be immediately life-threatening or result in death or hospitalization but may jeopardize

the subject or may require medical or surgical intervention to prevent one of the other outcomes listed in the above definition. These should also be considered serious. Examples of such events are invasive or malignant cancers, intensive treatment in an emergency room or at home for allergic bronchospasm, blood dyscrasias, or convulsions that do not result in hospitalization, or development of drug dependency or drug abuse.

8.1.3. Adverse Events of Special Interest

In prior clinical studies, the following AEs have been identified as AEs of particular clinical importance and will be reported as AESIs in this study; in each case study drug may be discontinued, based on Investigator judgment, and may be restarted when the event resolves:

- Contact dermatitis: the study site should collect location, duration, size, associated symptoms (itching, burning, pain), severity (mild, moderate, severe), and photograph the affected site (if possible). If the subject contacts the study site to report significant skin irritation at or near the site of study drug application between study visits, the subject should be brought in for an unscheduled visit, if possible.
- Folliculitis: the study site should collect the location, duration, size, associated symptoms (itching, burning, pain), severity (mild, moderate, severe), indicate whether pustular, and photograph the affected site (if possible).
- Headache: the study site should collect duration, severity (mild, moderate, severe), onset, and location (e.g., frontal, temporal, occipital, diffuse).

Additional AESIs may be identified by the Drug Safety Physician and if applicable by the Clinical Study Team Physician during the evaluation of safety data for the Clinical Study Report. For each AESI, a narrative may be written and included in the Clinical Study Report.

8.2. Classification of Adverse Events

8.2.1. Assigning Severity Rating for Adverse Events

8.2.1.1. Criteria for Determining Averse Event Severity

The Investigator will make an assessment of the severity of each AE and SAE according to the National Cancer Institute Common Terminology Criteria for Adverse Events (CTCAE), v. 5.0, 2017. For terms not specified with the CTCAE, the criteria in [Table 4](#) should be used to determine the grade severity.

Table 4: Criteria for Determining the Grade/Severity of Adverse Event Terms Not Specified by the National Cancer Institute CTCAE

Grade	Criteria
1	Mild; asymptomatic or mild symptoms, clinical or diagnostic observations only; intervention not indicated
2	Moderate; minimal, local, or noninvasive intervention indicated; limiting age-appropriate instrumental activities of daily living ^a
3	Severe or medically significant but not immediately life-threatening; hospitalization or prolongation of hospitalization indicated; disabling; limiting self-care activities of daily living ^b
4	Life threatening consequences; urgent intervention indicated
5	Death related to adverse event

CTCAE = Common Terminology Criteria for Adverse Events.

^a Instrumental activities of daily living refer to preparing meals, shopping for groceries or clothes, using the telephone, managing money, etc.

^b Self-care activities of daily living refer to bathing, dressing and undressing, feeding self, using the toilet, taking medications, and not bedridden.

Adverse event severity should be recorded in the appropriate section of the adverse event case report form and in the subject’s source documents.

8.2.1.2. Toxicity Management Criteria

8.2.1.2.1. Grade 1 or Grade 2 Adverse Event

Subjects who develop a Grade 1 or Grade 2 AE may continue investigational product at the discretion of the Investigator. Subjects who choose to withdraw from study due to a Grade 1 or 2 AE should have study withdrawal/follow-up evaluations completed.

8.2.1.2.2. Grade 3 Adverse Event

Subjects who develop a Grade 3 AE should be managed as follows:

- If the Investigator has compelling evidence that the Grade 3 AE has not been caused by investigational product, then dosing may continue after discussion with the Medical Monitor.
- Subjects who develop a Grade 3 AE that the Investigator considers related or possibly related to investigational product should have the investigational product discontinued. Subjects experiencing Grade 3 AEs requiring permanent discontinuation of investigational product should be followed weekly until resolution or stability of the AE and encouraged to have withdrawal study evaluations completed.

8.2.1.2.3. Grade 4 Adverse Event

Subjects who develop a Grade 4 AE should have investigational product permanently discontinued.

Subjects experiencing Grade 4 AEs requiring permanent discontinuation of investigational product should be followed weekly until resolution or stability of the AE and encouraged to have withdrawal study evaluations completed.

8.2.1.2.4. Other Management Criteria:

The Medical Monitor should be notified if any of the following occur:

- Severe signs or symptoms, or significant changes in any of the safety assessments, that put the safety of the subject at risk (eg, laboratory tests or vital signs, etc.) as judged by the Investigator.

8.2.2. Assigning Causal Relationship to Study Drug

The Principal Investigator is to make the causality assessment. Causality assessment is not to be delegated; however, if delegation is unavoidable due to investigator inaccessibility, this must be recorded as a protocol deviation. The reasonable possibility of the relationship of an adverse event to study drug is to be assessed with careful medical consideration at the time of evaluation of an adverse event. The following definitions are to be used for the relationship of the adverse event to study drug:

- **Related:** A clinical event, including laboratory test abnormality, with a temporal relationship to study drug administration that makes a causal relationship plausible, unlikely attributed to concurrent disease or other drugs or chemicals, and that follows a clinically reasonable response on re-administration (rechallenge) or withdrawal (dechallenge), although information on drug withdrawal may be lacking or unclear.
- **Not related:** A clinical event, including laboratory test abnormality, with a temporal relationship to study drug administration that makes a causal relationship improbable and/or in which other drugs, chemicals, or underlying disease provide a plausible explanation.

Any AEs /SAEs assessed as related to study participation (eg, protocol-mandated procedures, invasive tests, or change in existing therapy) or related to study drug will be recorded from the time a subject consented to participate in the study up to and including any follow-up contact.

All AEs, whether related to study drug or not, must be fully and completely documented on the AE page of the eCRF and in the subject's clinical record. In the event a subject is withdrawn from the study because of an AE, the primary reason for withdrawal (ie, due to an AE) must be recorded on the eCRF as such.

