### **12.9.1 Adverse Events**

AE terms will be coded using the MedDRA dictionary. A treatment-emergent AE (TEAE) is defined as an AE that starts after the first dose of study medication. For subjects not rolling over to Open-label study, all reported AEs will be included in the Double-Blind phase summaries. For subjects rolling over to the Open-label study, all AEs with an onset date on or before the Week 12 visit date will be included in the Double-Blind phase summaries.

If relationship to treatment is missing, the event will be conservatively treated as related to study drug. Missing severity will be imputed to the highest severity level (most severe).

All AEs will be listed by treatment and by subject, detailing the verbatim term given by the investigator, the preferred term (PT), system organ class (SOC), onset date and time, end date and time, duration (days), CTCAE grade, outcome, relationship to study drug/treatment, action taken with study drug/treatment, other action taken to treat the event, seriousness and criteria for seriousness. Serious AEs (SAEs), TEAEs leading to study discontinuation, TEAEs related to study drug will also be listed separately. The following adverse event of special interest (AESIs) will be identified and listed separately: contact dermatitis, folliculitis, and headache.

AEs will be summarized by treatment and overall as incidence rates of:

- Any AE
- Any TEAE
- Any AESIs
- Any treatment-related TEAE, including definitely, probably, and possibly related
- Any TEAE leading to study drug discontinuation
- Any SAE (non-Fatal)
- Any serious TEAE
- Death
- Treatment-related Serious TEAE
- Serious TEAE leading to study drug discontinuation

Individual PTs will be summarized by treatment according to the following:

- All TEAEs by SOC in alphabetical order and PT in descending order of combined frequency (also for treatment-related TEAEs, TEAEs leading to study discontinuation and serious TEAEs)
- All TEAEs by SOC, PT, and maximum CTCAE grade
- All TEAEs by SOC, PT, and maximum causality (not related, related) to the study drug

In addition, TEAEs and serious TEAEs will be summarized by SOC (alphabetical order) and PT (descending order) for the following subgroups:

- Age (<65 and >= 65 years old)
- Sex
- Race (White, Other)

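### Protocol 8.2.2 codes an event with both a plausible drug cause and a plausible alternative as not related, while SAP 12.9.1 says its treatment-related line includes possibly related events

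*Protocol*

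**What the plan says.** Protocol 8.2.2 opens with the standard for the judgement: "The reasonable possibility of the relationship of an adverse event to study drug is to be assessed with careful medical consideration". It then fixes the scale: "The following definitions are to be used for the relationship of the adverse event to study drug". Two definitions follow.

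- *Related* needs a plausible causal link in time, and the event must be "unlikely attributed to concurrent disease or other drugs or chemicals".
- *Not related* covers events whose timing makes a causal link improbable, "and/or in which other drugs, chemicals, or underlying disease provide a plausible explanation".

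SAP 12.9.1 lists among the overall incidence rates "Any treatment-related TEAE, including definitely, probably, and possibly related". Its table by system organ class and preferred term uses two levels: "All TEAEs by SOC, PT, and maximum causality (not related, related) to the study drug". The same section counts an event with missing causality as related. SAP 13 declares no change to the causality scale.

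Other protocol sections use other terms. Section 8.2.1.2.2 speaks of a "Grade 3 AE that the Investigator considers related or possibly related to investigational product". Section 8.5 uses a possibly-related test for serious events associated with a pregnancy. Section 4.6.1 refers to Grade 3 or 4 events that are causally related and points to 8.2.2.

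**The concern.** An event that the cream could plausibly have caused, but that something else could also explain, is the ordinary doubtful case. A reasonable-possibility standard keeps it as related, and the SAP's overall line tells the reader that it is in the count. The two prescribed definitions put it in the other category.

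Such events are to be expected here. Skin reactions to the cream may present as erythema (Protocol 1.3.1.1), and erythema is also one of the signs on which psoriasis is graded (Protocol 6.2.1.1). Underlying disease is thus a ready alternative explanation.

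Investigator-assessed related TEAEs are a protocol-specified summary (Protocol 10.4.3). The SAP adds related-TEAE listings and tables, a related serious TEAE count, and the highest causality level for each AESI. The trial is described as pivotal and intended to support registration (Protocol 1.1.2), so the label on those tables should match the rule that produced the data.

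**Working it through.** The plan gives no figure to reproduce. The check sets the definitions side by side, assuming that a plausible drug cause amounts to a reasonable possibility.

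| Drug cause | Other cause | 8.2.2 definitions | 8.2.2 opening standard | SAP overall line |
|---|---|---|---|---|
| plausible | unlikely | Related | related | counted |
| plausible | plausible | Not related | related | counted, as possibly related |
| improbable | plausible | Not related | not related | not counted |
| improbable | unlikely | Not related | not related | not counted |

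Only the second row conflicts. Such an event fails *Related*, because the alternative is not unlikely. It meets *Not related* through the *or* in the and/or clause. Reading that clause as *and* does not help: the event would then meet neither definition.

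**Outputs affected.** These are the treatment-related TEAE rate, table and listing; the related serious TEAE count; and the causality line of the AESI summaries. Counts of all TEAEs, all serious events and all AESIs do not use this coding. Nor does the Kaplan-Meier figure of time to first AESI.

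**Size.** Let N be the number of subjects that the SAP's wording would count as having a treatment-related TEAE. Let f be the share of them whose every qualifying event falls in the second row and is coded *Not related*. SAP 12.9.1 counts a subject once, so the reported number is (1 − f) × N. For N = 100:

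- f = 0: 100 reported, no understatement
- f = 0.10: 90 reported, 10% understatement
- f = 0.25: 75 reported, 25% understatement
- f = 0.50: 50 reported, 50% understatement

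These values of f are assumptions. The documents contain nothing from which to estimate it.

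**Between arms.** Both arms use the same definition. If f were equal in the two arms, the ratio of related rates would be unchanged, and the difference would become (1 − f)p_T − (1 − f)p_V = (1 − f)(p_T − p_V). Here p_T and p_V are the rates under the SAP's wording.

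**Missing causality.** The missing-as-related rule works upward, but only for blanks. It does not recover an event actively coded *Not related*. A blank is counted as related, while an event judged to have a plausible drug cause and a plausible alternative is not.

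**The case against.** Several points on the other side stand.

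- The SAP's three graded levels look like leftover text, and an unused level adds zero to a count. The SAP mismatch is therefore a labelling error. Any downward pressure comes from the 8.2.2 definitions.
- The alternative must plausibly explain the event being judged. That a type of event has other known causes is not enough.
- The named risks are also captured without causality coding. Contact dermatitis, folliculitis and headache are AESIs with their own summaries, local irritation is scored by investigator and subject, all-causality TEAEs are shown by blinded arm, and safety is not formally tested.
- A strict two-level scale is a legitimate choice. It cannot, however, sit under a reasonable-possibility standard or feed a line said to include possibly related events.

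Three stronger readings are tempting, but the documents do not support them. A reader might infer that treatment-related TEAEs *are* understated; the text shows only that they can be, since f is unknown. A reader might infer that a possibly-related event cannot be recorded; the eCRF causality field is not in the documents, so all that can be said is that 8.2.2 has no such category. A reader might try to size the loss from the headache rate above 10% in Protocol 1.1.1. That rate comes from studies of an earlier formulation, is not limited to drug-related events, and says nothing about how many cases had a plausible alternative.

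**Conclusion.** The inconsistency is real and should be corrected. As written, 8.2.2 contradicts its own opening standard, and SAP 12.9.1 describes its treatment-related line by levels that the protocol does not define. The related-TEAE, related serious TEAE and AESI causality summaries can fall below the SAP's stated definition. The AESI, local tolerability and all-causality data limit the consequence, but they do not correct those summaries.

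The amount is unknown. The conclusion rests on sites applying the 8.2.2 definitions literally and on the eCRF following them. Efficacy and all-causality safety results are not touched.

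**What to change.** 1. In Protocol 8.2.2, align both definitions with the section's reasonable-possibility standard, so that a plausible alternative alone is not sufficient for *Not related*.
2. In SAP 12.9.1, have the treatment-related line name the categories actually recorded, after checking the eCRF field.
3. If events are already coded under the current wording, correct the SAP label and state the definition used in the report. SAP Amendment 2 (04MAY2020) already deals with visits altered by COVID-19, which suggests the trial was under way.
4. Protocol 4.6.1, 8.2.1.2.2, 8.2.2 and 8.5 use different causality terms and must be reconciled. Because 4.6.1 cites 8.2.2, a changed definition also bears on that section. No discontinuation rule is proposed here.

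The cost is a protocol wording change, a note to sites and one SAP line. The related rate would be somewhat higher in both arms. A mid-study change would also leave two causality standards in one dataset unless earlier events are re-queried while still blinded, which is additional site work.
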